9.7 Handling of Missing Data

Sensitivity analyses of the primary safety endpoint and primary performance endpoint will be done using methods for single imputations and multiple imputations (MI) for the ITT population and the PP population.

9.7.1 Device Holiday

A Device Holiday is defined as a period of time where a subject is unable to or does not perform treatments on the HemoCareTM Hemodialysis System per the prescribed schedule. A Device Holiday may result in the extension of a subject's participation in the study in order to receive the required number of treatments in a given period. Any time a patient is not able to treat at home, they will return to their training facility or another in-center facility as determined by the site Principal Investigator.

Reasons for a Device Holiday are inclusive of, but not limited to:

- Subject hospitalization
- Missed treatment
- · Required device servicing

Boil-water advisory/order

9.8 Other Assessments or Analysis

Subgroup analysis may be performed using for example subgroups defined from age (below 55 years versus 55 years or more), diabetes status (diabetic versus non- diabetic). Where applicable, the potential difference within a subgroup may also be investigated in the regression model by including the subgroup as covariate in the model.

For primary safety endpoint, a potential time trend during each Evaluable Period will be investigated by including the time since start of the Evaluable Period in the model.

Details regarding further AE analyses, as well as other assessments or analyses are included in the SAP.

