With an underlying goal to have at least 1000 HemoCareTM Hemodialysis System treatments in both Evaluable Periods, at least 30 subjects will enter the Assisted Evaluable Period. No more than 25% of the total study subjects who complete the study may be enrolled at one site. Each patient is expected to contribute at least 68 evaluable treatments to the study (at least 34 in each Evaluable Period).

Based upon the number of treatments and the expected rate of adverse events, the current study design is under-powered to detect a clinically meaningful (less than 10%) non-inferiority margin for the Unassisted Evaluable Period.

For the primary performance endpoint, 'success' is defined as a subject who has all stdKt/Vurea measures in an evaluable period greater than or equal to 2.0. Several sets of simulation samples were generated (2,000 samples per set) assuming a rate of success between 95% and 99.5% and no actual difference between the two Evaluable Treatment Periods. The success rate of the 2 periods were compared and the CI interval for the differences were calculated. With 30 subjects in each Evaluable Period, a margin of 10% will provide 91% power to declare non-inferiority if the actual success rate is 99% and 83% power if the actual success rate is 98%.

Analysis Populations:

The Intent-to-Treat (ITT) population set will include all subjects who have used HemoCareTM Hemodialysis System at least once during the Assisted Evaluable Period.

The Per Protocol (PP) population will include all subjects not having any enrollment violations and receiving at least 34 treatments in each Evaluable Period. The PP population will be used as sensitivity analyses of the primary safety endpoint and primary performance endpoint.

Poolability of the data will be examined by assessing the heterogeneity of the primary endpoint results across sites with 5 or more subjects enrolled.

Primary Safety Endpoint:

The AE rate per 100 HemoCare™ Hemodialysis System treatments of Unassisted Home Evaluable Period will be compared to that of the

Assisted Evaluable Period and a two-sided 90% CI will be generated for the rate ratio (λ_2/λ_1) comparing the relative difference in AEs for the two Evaluable Periods using a negative binomial regression model.

Primary Performance Endpoint:

Performance of the HemoCare™ Hemodialysis System will be assessed by weekly stdKt/Vurea that will be collected every two weeks during each Evaluable Period.

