9.1 General Considerations

Further details of the planned statistical methods presented below will be provided in the study statistical analysis plan (SAP). The purpose of the SAP is to further elaborate the statistical methods described in the protocol and describe analysis conventions to guide the statistical programming work. Any changes to the final SAP will be documented. Unless otherwise specified, treatment effects will be evaluated based on a 2-sided significance level of 0.050 (when rounded to 3 decimal places)

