9.4 Primary Endpoints

9.4.1 Primary Safety Endpoint

The primary safety analysis will be to compare the Unassisted Home Evaluable Period AE rate per 100 HemoCareTM Hemodialysis System treatments against the Assisted Evaluable Period AE rate per 100 HemoCareTM Hemodialysis System treatments. A two-sided 90%

CI will be generated for the rate ratio $(\lambda 2/\lambda 1)$ comparing the relative difference in AEs for the two scenarios using a negative binomial regression model. The analysis will be carried out on the ITT population. The response variable is the total number of AEs. The model will include an indicator variable that is equal to one if treatment is "Assisted Evaluable Period" and zero otherwise. In addition, the log of the number of treatments will be included as an offset variable in the model and a subject specific random effect for treatment period will be included with covariance structure specified as "unstructured."

Let $\lambda_i = \frac{n_{aei}}{N_{txi}}$ be the rate of adverse event during treatment $i = \{a \text{ for assisted treatment} \}$ $\{a \text{ for unassisted trreatment} \}$

Where:

 $n_{aei} = Number \ of \ adverse \ event \ during \ treatment \ i, and \ N_{txi} = Number \ of \ treatment \ type \ i$

Given a non-inferiority margin δ ,

$$H_0: \frac{\lambda_u}{\lambda_a} > 1 + \delta$$
 $H_1: \frac{\lambda_u}{\lambda_a} \le 1 + \delta$

The Negative Binomial distribution will be used as a link function with the log transformation will be used to estimate the ratio and it's Confidence Interval. The logarithm of the Number of treatment for each treatment modality will be included as an offset term to account for any potential unpredicted unbalance between the two modalities sample sizes. If the Negative Binomial model fail to converge, the Poisson distribution with Scale =Dispersion will be adjusted.

Let UCI be upper boundary of the $\frac{\lambda_u}{\lambda_a}$ ratio confidence interval. H_0 is rejected if UCI $\leq 1 + \delta$ resulting in accepting H_1 and concluding Unassisted treatment are not inferior than assisted treatment.

The same analysis will be conducted using the PP population.

The evaluation of the primary safety endpoint will be based on the results from the ITT population and the PP population.

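### The regression route in Section 9.8 adds the subgroup only as a covariate, so that model still gives one common Unassisted/Assisted rate ratio and cannot show whether the ratio differs by age or diabetes.

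*Combined protocol and SAP*

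**What the plan says.** Section 9.8 offers two optional routes to subgroup results. The first is general: "Subgroup analysis may be performed using for example subgroups defined from age (below 55 years versus 55 years or more), diabetes status" and so on, with no method described. The second, introduced as a supplement and only where applicable, is that "the potential difference within a subgroup may also be investigated in the regression model by including the subgroup as covariate in the model". Neither sentence names a period-by-subgroup interaction.

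The regression model for safety is in Section 9.4.1. It is a negative binomial model for the AE count with these parts:

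- Period: "The model will include an indicator variable that is equal to one if treatment is" Assisted, and zero otherwise.
- Exposure: "the log of the number of treatments will be included as an offset variable in the model".
- Subject: "a subject specific random effect for treatment period will be included", with unstructured covariance.

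The Protocol Summary adds that "a two-sided 90% CI will be generated for the rate ratio". The only heterogeneity check named for the primary endpoints is poolability across sites (Section 9.3). Section 9.8 refers to the SAP for further analyses, and the combined document contains no separate SAP text on this point.

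**The concern.** The safety objective is to compare the Assisted and Unassisted periods. The natural subgroup question is therefore whether that comparison comes out differently in older subjects or in diabetics. Each subject is meant to contribute to both periods, and age group and diabetes status belong to the subject, not to the period. A main effect for such a factor raises or lowers the AE rate in both periods by the same multiple. It answers a different question: whether diabetics, say, have more AEs in general.

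The risk is misreading in both directions. A significant covariate could be reported as a subgroup difference when the period ratio is the same in both groups. A non-significant covariate could be reported as consistency when the ratios differ. This has some weight here because Section 9.2 says the study is under-powered for a clinically meaningful safety margin and rests the safety decision on clinical judgement of AE rate and type. Supporting analyses will feed that judgement.

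**Working it through.** Section 9.8 states no figure, so there is none to reproduce. The check is of what the model can estimate.

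**Structure.** Let A = 1 for Assisted and 0 for Unassisted, S = 1 for the subgroup, and N the number of treatments. The covariate model is

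log(mean AEs) = log N + b0 + b1·A + c·S + subject effects.

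The Unassisted/Assisted ratio is exp(−b1) whether S is 0 or 1. The coefficient c is the log ratio of AE levels between subgroups. Adding d·A·S makes the ratio exp(−b1) when S = 0 and exp(−b1−d) when S = 1. Only d measures a difference in the ratio.

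**Inputs from the documents.** 30 subjects and 34 treatments per subject per period (Section 9.2), and a 90% CI.

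**Assumptions not in the documents.** An even split of 15 and 15, 5 AEs per 100 treatments in the Assisted period, and true ratios of 1.0 (S = 0) and 2.0 (S = 1).

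**Expected counts.** Each cell has 15 × 34 = 510 treatments.

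| | Assisted | Unassisted |
|---|---|---|
| S = 0 | 25.5 | 25.5 |
| S = 1 | 25.5 | 51.0 |

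**Fits to these counts (Poisson, equal exposure).**

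- Period only: 76.5/51 = 1.50. SE of the log = √(1/51 + 1/76.5) = 0.181, so the 90% CI is 1.11 to 2.02.
- Period + subgroup: 1.50 with the same CI. The covariate is also 76.5/51 = 1.50, but it is a ratio of AE levels between subgroups.
- With interaction: 25.5/25.5 = 1.00 (90% CI 0.63 to 1.59) and 51/25.5 = 2.00 (90% CI 1.34 to 2.98). The ratio of ratios is 2.00, with SE of the log = √(3/25.5 + 1/51) = 0.370 and 90% CI 1.09 to 3.68.

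The common ratio can move when the covariate is added. With a negative binomial fit (dispersion 0.5) it goes from 1.50 to 1.45. With 30% less exposure in the S = 1 Unassisted cell it goes from 1.41 to 1.46. In every case it remains one ratio for both subgroups.

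**What each test responds to.** 3,000 simulated trials per scenario were run at two-sided 0.05, with a log-normal subject effect of SD 0.5. The covariate test compared mean total AEs between subgroups. The interaction test compared log ratios from pooled counts. Both are simple stand-ins for the terms of the full mixed model.

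| Scenario | Covariate significant | Interaction significant |
|---|---|---|
| Same ratio, S = 1 has twice the AE rate | 79% | 4% |
| Ratios 1.0 and 2.0, equal overall AE rates | 6% | 42% |
| Ratios 1.0 and 2.0, equal Assisted rates | 36% | 51% |

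The first two rows carry the point: the covariate reacts to AE level and is at about its nominal error rate when only the ratio differs.

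**Power of the interaction for a doubling, even split.** Section 9.1 sets a default of 0.05, and 0.10 matches the 90% CI, so both levels were looked at. Simulated power at 0.10:

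| AEs per 100 treatments | Same period effect for all within a subgroup | Period effect varies by subject (SD 0.5) |
|---|---|---|
| 10 | 84–85% | 71% |
| 5 | 64% | 50% |
| 2 | 39% | 35% |

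At 0.05 and 5 per 100, the simulations above gave 42% to 51%. The combination of 2 per 100 and 0.05 was not simulated. By normal approximation the counts are 10.2, 10.2, 10.2 and 20.4, SE = √(3/10.2 + 1/20.4) = 0.586, z = ln 2/0.586 = 1.18, and power is about 22%.

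**The case against.** Several points can be made for the plan.

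- **The covariate is not the only route.** The preceding sentence allows subgroup analysis, which is most naturally read as running the comparison within each subgroup. That would give separate ratios. This stands, and it rules out the stronger inference that Section 9.8 leaves no way of seeing a subgroup-specific ratio. What is absent is a described method for that route and any comparison of the ratios.
- **The covariate does not always leave the ratio exactly unchanged.** A reader might infer that it does, but this is exact only for Poisson data with balanced exposure. The plan specifies a negative binomial model and a minimum, not a fixed, number of treatments. The safe statement is that one common ratio is estimated.
- **The sentence may mean a difference in AE level between the subgroup categories.** A covariate does address that. The wording permits it, but it is not the period comparison that the study is built on.
- **The random period effect could absorb variation in the ratio.** It can, and it may widen the CI, but it does not tie the variation to age or diabetes.
- **Detail may sit in a separate SAP.** It may. The text available names no interaction and no heterogeneity test by age or diabetes.
- **An interaction test in 30 subjects is weak.** This stands. The 85% figure belongs to the most favourable setting tried and should not be read as the expected yield.

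**Conclusion.** The point holds for the regression route of Section 9.8. With one period indicator and a subgroup covariate, the model cannot show whether the Unassisted/Assisted ratio differs by age or diabetes, because the covariate term tests AE level. This follows from the form of the model and does not depend on the simulation settings. The illustrative sizes do depend on them: one ratio of about 1.5 in place of 1.0 and 2.0 rests on the assumed AE rate, even split and true ratios.

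The consequence is modest. The analysis is optional, its subgroups are given as examples, and it feeds no decision rule. A reader might infer that the primary safety result is compromised. The documents do not support that, since the primary ratio is specified without any subgroup term.

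**What to change.** Amend the second sentence of Section 9.8 so that, where the regression route is used, the model includes the subgroup and its interaction with period. Report the Unassisted/Assisted rate ratio with 90% CI for each subgroup level, plus the interaction estimate and its CI, labelled exploratory. The choice to run subgroup analyses can stay optional.

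The cost is one sentence and one model term, with no new data. The drawback is low precision. With about 30 subjects, power for a doubling is roughly 35% to 85% across the settings simulated, and lower still at 2 AEs per 100 with alpha 0.05. The text should therefore put the weight on estimates and intervals, and say that a non-significant interaction is not evidence that the ratios are alike.

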9.9 Interim Analysis

An interim analysis is not planned for this study

10 Data Management, Quality Control and Quality Assurance

10.1 Clinical Database

The designated CRO will be responsible for activities associated with the data management of this study. This will include setting up a relevant database and data transfer mechanisms, along with appropriate validation of data and resolution of queries. Data generated within this clinical study will be handled according to the relevant standard operating procedures (SOPs) of the data management and biostatistics departments of sponsor or the designated CRO.

Study centers will enter data directly into an EDC system by completing the CRF via a secure internet connection. Data entered into the eCRF must be verifiable against source documents at the study center. Data to be recorded directly on the eCRF will be identified and the eCRF will be considered the source document. Any changes to the data entered into the EDC system will be recorded in the audit trail and will be FDA CFR 21 Part 11 compliant.

Medical coding will use Medical Dictionary for Regulatory Activities (MedDRA) for concomitant diseases and AEs and WHO Drug for medications.

Missing or inconsistent data will be queried in writing to the Investigator for clarification. Subsequent modifications to the database will be documented

10.2 Audits and Inspections

In addition to the routine monitoring procedures and in accordance with Good Clinical Practice (GCP) principles, GCP audits might well be performed by the Quality Assurance members of Sponsor/Designee.

These audits of clinical research activities are in accordance with applicable regulatory requirements, Sponsor/designee internal policies and procedures, to evaluate compliance with the principles of GCP. A Regulatory Authority may also wish to conduct an inspection (during the study or even after its completion). If a Regulatory Authority requests an inspection, the Investigator must immediately inform the Study Monitor of Sponsor/designee that this request has been made.

11 Administrative Considerations

11.1 Institutional Review Board or Research Ethics Board Approval

The responsible Institutional Review Board (IRB) or Research Ethics Board (REB) must be constituted according to the applicable local and national requirements of each participating location. The Sponsor or its designee will require documentation noting all names and titles of members who compose the respective IRB/REB. If any member of the IRB/REB has direct participation in this trial, written notification regarding his or her abstinence from voting must also be obtained.

The Sponsor or its designee will supply relevant documents for PIs to submit to their respective IRB/REB for the review and approval of the protocol. The Investigator will not enroll subjects into the study until the Investigator has received written approval for, or written favorable opinion on, the protocol, the informed consent document(s), and any planned recruitment aids from their IRB/REB. The IRB/REB approval must refer to the study by exact protocol title, number, and version date; identify versions of other documents (e.g., subject or care partner ICFs) reviewed; and state the approval date. The Investigator will make all required progress reports to their IRB/REB in writing in a timely manner and will obtain all required approvals in writing (at least annually in all cases) to continue to participate in the study.

The Investigator will promptly report to their IRB/REB any unanticipated problems associated with the study devices involving risks to subjects or others, whether encountered at their site or provided as a safety report by Sponsor/designee.

Sites must adhere to all requirements stipulated by their respective IRB/REB. The Investigator will promptly notify their IRB/REB of any planned protocol amendment and will not implement any protocol amendment until the IRB/REB has provided written approval of, or written favorable opinion on, the amendment.

11.2 Ethical Conduct of the Study

This study will be conducted in accordance with the ethical principles that have their origin in the Declaration of Helsinki (Edinburgh 2000), the ethical and quality standards of good clinical practice (ICH E6) and all applicable regulatory requirements and laws. The PI will provide all necessary information on the protocol and the study device to all physicians, nurses, and other personnel who participate in this study under the PI's supervision and will discuss this material with them as needed, to ensure that they are fully informed regarding the conduct of the study and the potential effects of the study device.

11.3 Compliance with Protocol and Protocol Amendments

The Investigator, and all physicians, nurses, and other personnel who participate in this study under the Investigator's supervision, will conduct the study according to the currently approved version of the protocol. In cases where the protocol is not followed, the site staff will document the reason for the deviation from the protocol and any corrective actions taken and/or preventative measures put in place to avoid future occurrences. Serious or repeated deviations from the protocol will result in termination of the Investigator's participation in the study.

Neither the Investigator, nor the sponsor, will amend or modify the protocol without notifying the other. Any protocol amendment must be approved by DEKA R&D Corp. and CVS Kidney Care, in writing, must be agreed to by the Investigator in writing, and must be approved by the Investigator's IRB/REB in writing prior to implementation of the amendment.

11.4 Subject Information and Consent

The nature of the study will be fully explained to each potential subject and care partner and voluntary, written (signed and dated) informed consent will be obtained from the subject and care partner prior to enrolling the subject in the study. No study-specific procedures will be performed prior to the Investigator or their designee obtaining written informed consent.

Preparation of the ICF is the responsibility of the Sponsor/Designee and must include all elements required by GCP and applicable regulatory requirements and must adhere to GCPs and to the ethical principles that have their origin in the Declaration of Helsinki (see Appendix 2 for the requirements of an informed consent statement). All ICFs must be reviewed by the Sponsor prior to IRB/REB submission. Only subjects with the initial intention to complete the study should be considered for entry into the study.

The PI must provide the subject/care partner or a legal representative with a copy of each ICF and written information about the study in English only. The language must be nontechnical and easily understood. The PI should allow the time necessary for the subject or the subject's legal representative to inquire about the details of the study after which the ICF must be signed and

personally dated by the subject or by the subject's legally acceptable representative and by the person who conducted the informed consent discussion. The subject or a legal representative should receive a copy of the signed ICF and any other written information provided to the study subject prior to the subject's participation in the trial. The PI must furnish the Sponsor or its designee with a copy of each IRB/REB-approved ICF to be used in this study prior to the commencement of the study.

11.5 Subject Confidentiality

All subject information, medical records, and laboratory data will be kept confidential.

Information and data may be discussed, analyzed, and reported; however, code numbers will identify the subject on the eCRFs and in any reports, and the subject's identity will be kept confidential.

11.6 Protocol Violations/Deviations

Protocol violations/deviations will be documented in source for transmission into a tracking system. The clinical team will review deviations at a study level on a regular basis for issues and resolution.

11.7 Access to Source Documentation

Monitoring visits will occur at regularly scheduled intervals at the investigational site to allow for verification of source documents and comparison of source data with the information recorded on the eCRFs.

Representatives of the Sponsor, or its designee, must be allowed to visit the study site regularly to assess the data quality and the integrity of the study. These representatives will review study records on site and directly compare these with the source documents, discuss the conduct of the study with the PI, and verify that the facilities remain acceptable. In addition, the study may be evaluated by the Sponsor's internal auditors or a designee, and/or by government inspectors, who must be allowed access to eCRFs, source documents, and other study files.

The PI or a designated member of the PI's staff must be available at some time during monitoring visits to review data and resolve any queries and to allow direct access to the subject's records (e.g., medical records, office charts, hospital charts, and study-related charts) for source data verification. The eCRFs should be completed prior to each visit and be made available to the monitor so that their accuracy and completeness may be checked.

If an onsite visit is not possible due to public health or patient safety concerns, the site must provide electronic copies of source documentation to enable a remote monitoring visit, to ensure continued review of data quality and integrity of the study. The Sponsor or designee will work with the site

to enable this according to all federal, local, and institutional Patient Health Information protective measures.

This study may be subject to an independent audit at the investigational site, which will be conducted by independent auditors. Full consultation with appropriate personnel will be made prior to and during such audit. The PI must be available during the audit. If the PI is contacted by any regulatory authority regarding an audit for this study or any other study, the PI will contact the Study Manager and Medical Monitor immediately.

